### Available Alternative Opportunities/Treatments

Describe alternative treatments or opportunities that might be available to those who choose not to participate in the study, and which offer the subject equal or greater advantages. If applicable, this should include a discussion of the current standard of care treatment(s).

N/A

[Back to Top](#)

### Records, Privacy, and Confidentiality

Specify where the data and/or specimens will be stored and how the researcher will ensure the privacy and confidentiality of both. Specify who will have access to the data/specimens and why they need access.

Describe how data will be managed after the study is complete:

- If data/specimens will be maintained, specify whether identifiers will be removed from the maintained information/material.
- If identifiers will not be removed, provide justification for retaining them and describe how you will protect confidentiality.
- If the data/specimens will be destroyed, verify that this will not violate [retention policies](#) and will adhere to applicable facility requirements.

If this study will use de-identified data from another source, describe what measures will be taken to ensure that subject identifiers are not given to the investigator.

If applicable, describe procedures for sharing data/specimens with collaborators not affiliated with UK.

For additional considerations:

[Return of Research Results or Incidental Research Findings](#)

[HIPAA policies](#)

[FERPA policies](#)

[Procedures for Transfer agreements](#)

[Information regarding multi-site studies](#)

[NIH Genomic Data Sharing \(GDS\) Policy](#)

[Digital Data](#)

There will be no biologic material collected from pregnant women, as there are no invasive procedures being performed as part of the study. Women will continue to receive prenatal care throughout the course of pregnancy, just as they would have otherwise received regardless of study participation. While we will be using some of the clinical data that is relevant to the prenatal care of pregnant women, study participants will be undergoing these investigations as part of their prenatal care and not separately for the purposes of the study alone.

Some of the research materials to be collected includes gestational outcomes data, including but not limited to: details of maternal prenatal care, labor and delivery outcomes, details pertaining to the course of their OUD in pregnancy and details pertaining to individual patient MAT course, as well as neonatal data including hospital course, Finnegan scoring, incident NAS, neonatal treatment and follow up. These will be abstracted from a review of the standardized and template based electronic medical record system. These will be collected and stored in a HIPAA compliant safe and secure environment by personnel specifically trained in the handling of PHI.

Healthcare related data that will be collected will be stored in a secure, password protected electronic file on a single computer workstation with limited access. Similarly, all paper based documentation bearing identifying information will be stored in a secure locked filing cabinet under the PI's supervision. All data will be De-identified by stripping it of all identifiable PHI at the time of collection. Hence the data that will be used for analyses and review will be entirely De-identified, with study participants being referenced only through randomly generated numbers assigned to each study participant. This is being done to ensure the maintenance of confidentiality for the study participants and safety with regard to the use of healthcare data.

Healthcare related data will be collected from study participants and stored in a secured, password protected electronic file on a single computer workstation with limited access - solely to authorized study personnel as decided by the study PI. Similarly, all paper based documentation bearing patient identifying information (e.g. consent forms) will be stored in a secure locked filing cabinet under the PI's supervision with access granted solely to authorized study personnel as decided by the PI. All data will be de-identified by stripping it of all identifiable PHI at the time of collection. Hence, the data used for analyses and review will be entirely de-identified, with study participants being referenced only through randomly generated numbers assigned to each study participant. This is being done to ensure the maintenance of confidentiality for the study participants and safety with regard to the use of healthcare data. We do not anticipate any risks for prisoner participants beyond those of non-prisoners. This is a minimal risk study of prenatal education for women with OUD, the primary risk for all participants is breach of confidentiality. All participants are already receiving treatment for OUD, so there is no additional risk related to being identified with a substance use disorder.

**UK IRB policies** state that IRB-related research records must be retained for a minimum of 6 years after study closure. Do you confirm that you will retain all IRB-related records for a minimum of 6 years after study closure?

Yes  No

## Payment

Describe the incentives (monetary or other) being offered to subjects for their participation. If monetary compensation is offered, indicate the amount and describe the terms and schedule of payment. Please review [this guidance](#) for more information on payments to subjects, including restrictions and expectations.

Participants will be provided with gift cards based on participation at five prescribed time points that are tied to data collection and essential monitoring. The timepoints are: 1. initial enrollment and consent to participate within the project (\$50 gift card), 2. 28-32 week prenatal data collection (\$50 gift card), 3. report and receipt of infant measures upon delivery (\$50 gift card), 4. post-delivery data collection and receipt of measures on participant and baby at three (3) months (\$50 gift card), and 5. a final post-delivery data collection and receipt of measures on participant and baby at six (6) months (\$50 gift card). In addition, those patients who participate in the in- depth qualitative interview process (n=33) will be offered an addition participation incentive (\$50 gift card).

Following enrollment, participants will be informed about the opportunity to recruit other potential participants to the PATHHome Trial. Participants will be asked to share contact information for study staff and the partner clinic with potentially interested participants in their networks. Should a participant referral result in a confirmed study enrollment, the referring participant will receive a \$50 gift card.

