**Attachments****Informed Consent Process:**

Using active voice, describe how investigators will obtain consent/assent. Include:

- the circumstances under which consent will be sought and obtained
- the timing of the consent process (including any waiting period between providing information and obtaining consent)

- who will seek consent
- how you will minimize the possibility of coercion or undue influence
- the method used for documenting consent
- if applicable, who is authorized to provide permission or consent on behalf of the subject
- if applicable, specific instruments or techniques to assess and confirm potential subjects' understanding of the information

Note: all individuals authorized to obtain informed consent should be designated as such in the E-IRB "Study Personnel" section of this application.

Special considerations may include:

- Obtaining consent/assent for special populations such as children, prisoners, or people with impaired decisional capacity
- *Research Involving Emancipated Individuals*  
If you plan to enroll some or all prospective subjects as emancipated, consult with UK legal counsel **prior to submitting this application to the IRB**. Include research legal counsel's recommendations in the "Additional Information" section as a separate document.
- *Research Involving Non-English Speaking Subjects*  
For information on inclusion of non-English speaking subjects, or subjects from a foreign culture, see IRB Application Instructions for Recruiting Non-English Speaking Participants or Participants from a Foreign Culture.
- *Research Repositories*  
If the purpose of this submission is to establish a research repository describe the informed consent process. For guidance regarding consent issues, process approaches, and sample language see the [Sample Repository/Registry/Bank Consent Template](#).

Potential research subjects (those who are identified as being 6 - 32 weeks gestational age, with Opioid Use Disorder on Medication Assisted Therapy), will be approached for study enrollment by the trained study site research nurse. Study site research nurse (TBD) will consent patient for study enrollment. There is no required waiting period between informing prospective subject and obtaining consent. Only English speaking patients will be consented for study enrollment.

Patient participation or non-participation in the research protocol will not impact their routine clinical care in any way (prenatal or substance use care)

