#### Attachments

#### Subject Recruitment Methods & Advertising

Describe how the study team will identify and recruit subjects. Please consider the following items and provide additional information as needed so that the IRB can follow each step of the recruitment process.

- How will the study team identify potential participants?
- Who will first contact the potential subjects, and how?
- Will you use advertisements? If so, how will you distribute those?
- How and where will the research team meet with potential participants?
- If applicable, describe proposed outreach programs for recruiting women, minorities, or disparate populations.
- How you will minimize undue influence in recruitment?
- Attach copies of all recruiting and advertising materials (emails, verbal scripts, flyers, posts, messages, etc.).

For additional information on recruiting and advertising:

- [IRB Application Instructions - Advertisements](#)
- [PI Guide to Identification and Recruitment of Human Subjects for Research](#)

Participants will be recruited based on the following inclusion criteria: Pregnant women at 6-32 weeks gestational age; History of OUD; Who are receiving MAT and obtaining prenatal care at one of the 12 study sites. Patients will be identified by site research nurse (to be determined), viable pregnancy by ultrasound report will be confirmed and diagnosis of OUD and taking MAT will be confirmed. Patient will then be approached about possible recruitment in study. Each study site will have a contracted study nurse who will be identified, CITI trained and added to the IRB for patient recruitment. Although, not an inclusion or exclusion criteria, we have noted that a substantial proportion of potential study participants are under some type of criminal justice supervision at some point during their study participation. We have added a question to the study screener. Importantly, we will not screen or enroll women who are incarcerated in a detention center, easily identified by clothing worn by inmates and/or under escort or restrained by a guard or handcuffs.

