Telemedicine arm consultations will be provided by study personnel identified within this application including [name], [name] and [name].

**GROUP CARE ARM:** Study participants at the clusters randomized to the "group" arm will receive group care at 2 week intervals initiated from study enrollment. Group care sessions will be led by an on-site perinatal nurse facilitator and a local peer support specialist. The prenatal group sessions will be imparted in a structured fashion with each session lasting for 45-60 minutes. The content matter discussed will follow a rotating curriculum comprising 8 core sessions over a 16 week period, and will be repeated at each study site as long as there are enrolled active study patients. Once a patient is 8 weeks postpartum ,she will be seen monthly until 6 months postpartum. Data will be collected at each visit by trained study site personnel and entered in a secured online database (REDCap).

**TELEMEDICINE ARM:** Study participants at the clusters randomized to the telemedicine arm will receive the intervention through a telemedicine platform as part of the Kentucky Angels telemedicine program. The division of maternal fetal medicine has established a platform for obstetric outreach addressing perinatal issues pertaining to high risk pregnancies across Kentucky. As part of this cluster RCT, participants at study sites randomized to this arm will receive these telemedicine-based consultations with providers from perinatal nurse educators, peer support specialists, and substance abuse counselors at the University of Kentucky every two weeks until 8 weeks postpartum - and then monthly until 6 months post-partum. Should the patient have the need for additional sessions with a specialist, these will be provided . Data will be collected at each visit by trained study site personnel, and entered into a secured online database (REDCap). See data management plan for more information on the data storage.

The supplemental clinical care that patients will consist of a standardized rotating 8 topic patient education curriculum, including the following topics: 1. Treatment Options for Opioid Use Disorder 2. Smoking Cessation 3. Relapse Prevention Education 4. NAS Reduction Education 5. Breast Feeding Support/Education 6. Domestic Violence Education 7. Postpartum Depression 8. Birth Control/Family Planning.

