## SCHEDULE OF STUDY ASSESSMENTS

## ENROLLMENT/INTAKE

1. DSM-5 Criteria for Opioid Use Disorder
2. Edinburgh Depression Scale
3. Fagerstrom Nicotine Dependence
4. GAD-7 (Anxiety)
5. Adverse Childhood Experience (ACE)
6. Abuse Assessment Screen

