## 3rd Trimester

- 1) WHO QoL-BRF (Quality of Life measure)
- 2) Experience of Care and Health Outcomes (ECHO) - modified
- 3) Cornell Health Services Index (CHSI)
- 4) Fagerstrom Nicotine Dependence
- 5) Edinburgh Depression Scale
- 6) GAD-7

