14. Anxiety: GAD7 administered at intake, 3rd trimester, 3 and 6 months postpartum
15. Quality of life: WHO QoL-BRF administered in 3rd trimester, 3 and 6 months post-partum
16. Mother-Infant dyad status/Foster care requirement: retention of custody evaluated by patient interview at hospital discharge, 3 and 6 months postpartum
17. Maternal breastfeeding status: evaluated by patient interview at delivery, 3 and 6 months postpartum.

We will be collecting the following fetal data:

Fetal size per gestational age; Any genetic or structural anomalies; any other fetal complications.

We will be collecting the following neonatal data, including the following assessments:

Gestational age and weight at birth; 5 & 10min Apgar score; NICU/nursery hospital admission; NAS diagnosis & treatment requirement (primary outcome); NAS medication days; in-hospital growth (birth to discharge per day); other infant morbidities; total hospitalization length of stay; immunization compliance, ED visits, follow up with scheduled pediatric visits.

Data will be obtained via medical record review, patient interview, physician/staff report, review of state Medicaid data, and hospital discharge data by the study site research staff with the oversight of the UK-study team.

We will perform fidelity monitoring of intervention delivery. Research nurses/facilitators (group arm), providers (telemedicine arm), and all study participants will be asked to complete a fidelity form, similar to an evaluation form, at the end of each educational session. We will evaluate intervention fidelity by comparing provider and participant responses. If any discordance is identified between provider and participant responses for a given topic, additional training related to intervention delivery may be required.

In each arm, patients will be randomly selected to participant in a qualitative interview process at each participating site at the time of the 6 month postpartum follow-up. The interviews will be facilitated by Co-I [name], who has extensive experience using qualitative techniques with substance-involved patients in community based and treatment settings, with the assistance of research coordinators trained in qualitative interviewing techniques. Patients will be offered a fifty dollar stipend for their time to participate in the interview. 3 patients will be randomly selected from each participating site for a total of 33 interviews.

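### Does an undefined interval between intake and the third-trimester questionnaires spoil that reading for women enrolled late in pregnancy?

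*Combined protocol and SAP*

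**What the plan says.** The enrolment window is given three times with the same limits. Subject Recruitment Methods & Advertising has "Pregnant women at 6-32 weeks gestational age", the Informed Consent Process has "those who are identified as being 6 - 32 weeks gestational age", and the Study Population text agrees.

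The Schedule of Study Assessments lists an intake set, a set headed "3rd Trimester", and sets at 3 and 6 months postpartum. The third-trimester set has six instruments: WHO quality of life, ECHO, the Cornell index, Fagerstrom, Edinburgh and GAD-7. Three of these are also given at intake, for example the "Edinburgh Depression Scale". The maternal data list repeats the pattern, for example "GAD7 administered at intake, 3rd trimester, 3 and 6 months postpartum". Neither place gives a week range for the third-trimester visit or a minimum time since intake.

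A week range appears only under Payment, where gift cards are linked to "five prescribed time points that are tied to data collection and essential monitoring". The second of the five is the "28-32 week prenatal data collection".

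Under Research Procedures, women in the group arm "will receive group care at 2 week intervals initiated from study enrollment". The telemedicine arm has the same frequency, and a full curriculum is 8 sessions over 16 weeks. The SAP compares secondary outcomes between arms for superiority and names no time point for them.

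**The concern.** The last weeks of the enrolment window coincide with the dated prenatal data point. A woman who joins in those weeks could complete the third-trimester questionnaires at or soon after intake. Her Edinburgh, GAD-7 and Fagerstrom scores would then nearly repeat baseline. Her first quality-of-life, ECHO and Cornell readings would come when she had received little of the programme. ECHO asks about experience of care, so she would have little programme care to rate.

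The SAP does not exclude this reading from the between-arm tests. If many women were in this position, a real difference between group and telemedicine delivery would be diluted at this visit, and a null result there would be hard to read.

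**Working it through.** The plan states no interval from intake to this visit, so there is no figure of its own to reproduce. The check is interval arithmetic.

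**Are the two visits the same?** The documents do not say so in words. The payment point is the only prenatal data point after intake in either list, and the enrolment, 3-month and 6-month points match one to one. I take them as the same visit. The two descriptions are compatible, because 28-32 weeks lies inside the third trimester.

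**Gap from intake.** For enrolment at week g and a reading between 28 and 32 weeks, not before g, the gap runs from max(28, g) − g to 32 − g. The number of two-week intervals that fit is floor((32 − g)/2). Add one session if the first falls on the day of enrolment.

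| Enrolled at week | Gap (weeks) | Most two-week intervals |
|---|---|---|
| 6 | 22-26 | 13 |
| 20 | 8-12 | 6 |
| 24 | 4-8 | 4 |
| 28 | 0-4 | 2 |
| 30 | 0-2 | 1 |
| 32 | 0 | 0 |

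If 32 weeks is read as running to 32 weeks 6 days, the longest gap for a 28-week enrollee is 4.9 weeks. If the broader label governs, taken as 28-40 weeks (an assumption), gaps could reach 12 weeks for a 28-week enrollee and 8 for a 32-week enrollee, but the minimum is still 0.

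**Share of women.** The documents give no distribution of gestational age at enrolment. The window is 32 − 6 = 26 weeks. Share enrolled after 28 weeks, under three assumed shapes:
- uniform: 4/26 = 15.4%
- falling linearly to zero at 32 weeks: (4/26)² = 2.4%
- rising linearly from zero at 6 weeks: 1 − (22/26)² = 28.4%

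This is not the whole group. A woman enrolled at 27 weeks and assessed at 28 has a gap of 1 week. Anyone enrolled after 24 weeks can have a gap under 4 weeks, which is 8/26 = 30.8% if uniform.

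**Dilution.** Suppose a share s of women contributes no between-arm difference at this reading and the rest contribute a difference d. The expected contrast is then (1 − s)d. With s set to the three shares above, that is 0.976d, 0.846d and 0.716d. These figures assume that women enrolled after 28 weeks contribute nothing and that the share is equal in both arms.

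**What a 4-week minimum would do.** The earliest reading becomes max(28, g + 4).

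| Enrolled at week | Earliest reading (week) |
|---|---|
| 24 | 28 |
| 26 | 30 |
| 28 | 32 |
| 30 | 34 |
| 32 | 36 |

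A 28-week enrollee assessed at 32 weeks already complies, with the same two intervals as before. A 32-week enrollee moves from no intervals to two, which is 4/16 = one quarter of a curriculum cycle. The spread of gestational age at the reading doubles, from 28-32 to 28-36 weeks. Minimums of 6 or 8 weeks would put her at 38 or 40 weeks.

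**Later readings.** Fortnightly sessions run to 8 weeks postpartum. A woman enrolled at 32 weeks who delivers at 40 (an assumption) has 8 + 8 = 16 weeks by then, enough for one full cycle before the 3-month reading.

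**The case for a change.** The best case for a change is that it looks cheap: one line in the schedule and one in the payment text. Payment depends on the 28-32 week point, so sites have a practical reason to follow it. The SAP's example covariates do not include gestational age at enrolment or time since intake. Sites, not women, are randomised, so late enrolment could be more common in one arm. Recording attendance describes exposure but does not move the date of the questionnaire.

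The gap of 0-4 weeks stands, and so does the absence of a stated minimum. The rest is weaker. Nothing in the documents suggests that enrolment timing differs by arm; the window, curriculum and session frequency are common to both. Dilution of this kind pulls a superiority contrast towards the null and does not favour either arm. It would matter differently for noninferiority, but the SAP reserves that for the primary outcome, which is not measured at this visit.

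The line of text is cheap, but its consequences are not. Women who deliver before a delayed questionnaire would miss it, and that missingness is tied to preterm birth, itself a collected outcome. Reading everyone in a common gestational window is a reasonable choice, and trial statisticians could fairly prefer either arrangement.

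The firmer gap is that the SAP names no time point for secondary outcomes. That is a separate matter, and a minimum interval would not settle it.

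**Conclusion.** No change to the plan follows. Some women can complete the third-trimester questionnaires 0-4 weeks after intake if the payment window sets the timing. The consequence is confined to one secondary reading. All six instruments are repeated at 3 and 6 months postpartum.

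Under the three assumed enrolment shapes, and with late enrollees assumed to contribute nothing, the between-arm contrast at this visit shrinks to between 98% and 72% of its value, or 85% if enrolment is uniform. The true figure cannot be computed from the documents. It also depends on an analysis of this reading, which the SAP does not specify.

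Keeping a common gestational window is a fair trade-off. Analysts can fill what is left sensibly. Gestational age at enrolment has to be established to confirm eligibility, attendance at sessions is collected for each woman, and the SAP allows covariates where needed. Time from intake to this questionnaire can therefore be described by arm when the results are read, provided completion dates are kept with the survey data (an assumption).
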